14 The ‘Since Last Visit’ version of the scale will be used to assess suicidality since the last time the C-SSRS was administered. If at any time during the trial a patient has a suicidal ideation of type 4 or 5, or any suicidal behavior, the patient should be referred to a mental health professional (MHP).

15 Safety laboratory tests will include: Complete blood count (CBC) with platelet count and standard indices, chemistry panel (includes sodium, potassium, chloride, CO₂, albumin, total protein, glucose, blood urea nitrogen [BUN], creatinine (including eGFR), uric acid, aspartate aminotransferase [AST], alanine aminotransferase [ALT], gamma-glutamyl transferase [GGT], creatine phosphokinase [CPK], alkaline phosphatase, total bilirubin, direct bilirubin, lactate dehydrogenase [LDH], calcium, phosphorus), and urinalysis with microscopic analysis if positive findings on dipsticks warrant further examination. Safety laboratories will also include a coagulation profile (prothrombin time [PT] or international normalized ratio [INR], and partial thromboplastin time [PTT] also referred to as activated PTT [aPTT]).

16 A blood sample for PK will be drawn at the time points indicated before dosing, with dosing performed at the clinic. PK samples will be drawn with patients/caregivers being reminded there should be NO trial medication administration at home on the day of clinic visits; the drug will be administered in the clinic by the patient AFTER the PK sample is obtained. For the PK sample, the actual collection (clock) time will be recorded.

17 Any patient with a positive ADA will be followed every 3 months after the ADA sample analysis until resolution of the ADA.

18 A biomarker blood sample will be collected for metabolic, inflammation, metabolomic and/or proteomic biomarker analysis. This sample may not be analyzed. All samples are sent to a central laboratory. Additional details are described in the laboratory manual.

19 A daily question querying whether the patient completed their daily injection will be asked via electronic diary. Paper versions can be used, if needed.

20 Dispensing will be made by site staff, using the dispensation function in the Interactive Response Technology (IRT) system, as outlined in the SoA.

Dispensing may also be made directly to the patient if required and allowed by local regulations. At the Early Termination visit, only drug return will apply.

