8.9.8. Injection Site Examination

Injection sites will be carefully inspected, evaluated, and scored at the time points outlined in the SoA ([Table 1](#) and [Table 2](#)) during the trial period. The injection site evaluation will include identification and measurement of areas of erythema, edema, and induration, as well as the presence of localized pain, tenderness, and itching. A sample injection site evaluation form is included in [Appendix 4](#).

In addition, unscheduled evaluations may also be recorded as warranted by clinical conditions.

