10.3. Statistical Analyses

A separate SAP will be developed, which will include a more technical and detailed description of the statistical analyses described in this section.

The primary efficacy endpoint of the trial is the proportion of patients by genotype who demonstrate a significant clinically meaningful response (defined below) to setmelanotide at the end of Stage 1:

- For all patients: $\geq 5\%$ reduction in BMI from Baseline

The 95% exact confidence interval will be provided for the primary efficacy endpoint. The analyses of the efficacy endpoints in Stage 1 will be performed based on the safety analysis set, and the analyses of the efficacy endpoints in Stage 2 will be performed based on the FAS, which is defined as all patients randomized in Stage 2 who received at least 1 dose of trial medication (placebo or setmelanotide) in Stage 2 and have baseline data.

AEs/SAEs will be summarized with frequencies and percentages. A by-patient AE data listing including onset and resolution dates, verbatim term, preferred term, treatment, severity, relationship to treatment, action taken, and outcome will be provided.

Safety data including laboratory evaluations and vital signs assessments will be summarized by time of collection. In addition, change from baseline to any post-dose values will be summarized for vital signs and clinical laboratory results. Frequency of patients with abnormal safety laboratory results will be tabulated.

All safety analyses and summary tables will be based on the safety analysis set.

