APPENDIX 4. INJECTION SITE EVALUATIONS

Injection sites will be assessed at the time points outlined in the Schedule of Assessments (Table 1 and Table 2), and in the setting of any injection site reaction adverse experience. This assessment will consider severity and measurement (length and width if applicable) of any instance of erythema, edema, induration, itching, pain/tenderness or other relevant findings.

Local Skin Tolerability Assessment

Reaction	NONE	Mild	Moderate	Severe	Measurement (if applicable)
Erythema* ¹					
Edema*					
Induration* ¹					
Itching					
Pain or Tenderness					
Other: _____					

* If present, region will be measured, length and width as appropriate.

¹ In the event of severe erythema, defined as ≥ 10 cm, and/or induration of the injection area of the size of ≥ 10 cm and in the presence of fever defined as $\geq 38^{\circ}\text{C}$, or based on the Investigator's clinical judgement, the Investigator should contact the Sponsor and discuss therapeutic management of the patient and potential temporary drug discontinuation.

Initials: _____

APPENDIX 5. ADVERSE EVENTS: DEFINITIONS AND PROCEDURES FOR RECORDING, EVALUATING, FOLLOW-UP, AND REPORTING

Definition of Adverse Event (AE)

AE Definition

• An AE is any untoward medical occurrence in a patient or clinical trial patient, temporally associated with the use of trial treatment, whether or not considered related to the trial treatment.• NOTE: An AE can therefore be any unfavorable and unintended sign (including an abnormal laboratory finding), symptom, or disease (new or exacerbated) temporally associated with the use of trial treatment.

Events Meeting the AE Definition

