In general, unless otherwise specified, events or measurements happen before the randomization date are in Stage 1 and happen on or after the randomization date are in Stage 2. For patients who are not randomized, all events or measurements are in Stage 1. All events happening after visit 14 will not be considered as in Stage 2 for patients who enrolled into bridging visit unless otherwise specified.

D. Definition of Baseline

Baseline Definition

Baseline will be defined as the last non-missing measurement taken prior to the start of stage 1 open-label treatment administration. In the case where the last non-missing measurement and the reference start date coincide and time of measurement is not available, that measurement will be considered Baseline unless the assessment was scheduled to be post-study drug administration in the SOA. Change from baseline is defined as the post-baseline value minus the baseline value, unless specified otherwise. Percent change from baseline = $(\text{Change from Baseline}/\text{Baseline}) \times 100$.

Study Day

Study Day will be calculated from the reference start date within stage and will be used to show start/stop day of assessments and events. Reference start date is defined as the day of first dose (Day 1) in stage1.

Study Day will be computed as follows:

(Confidential)

- Study Day = (date of event - date of first dose in stage 1) + 1 if the date of the event is on or after the date of first dose.
- Study Day = (date of event - date of first dose in stage 1) if the date of the event is prior to the date of first dose.

E. Missing Data

Unless stated otherwise, missing data will not be replaced with imputed values. When relevant, sections below will address how missing data will be handled for the particular analyses.

Analysis Window

All measurements recorded at unscheduled or early termination visits will be mapped according to the windowed visits by actual study day. These records then will be used for analysis if the scheduled ones are missing. If more than one visit occurs within a single visit window, then the analysis will take the one closest to and before the target day. All scheduled assessments will be analyzed according to the protocol defined visits, regardless of the study day

Stage	Study Visit	Study Week	Study Day	Study Day Window
1	Enrollment Visit	1	1	1
1	Virtual Visit 2	2	14	Post-dose - 21
1	Virtual Visit 3	4	28	22 - 35
1	Virtual Visit 4	6	42	36 - 49
1	Visit 5	8	56	50 - 70

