1. The Baseline/Screening version of the scale is the initial form of the instrument to assess suicidality in a patient's lifetime. This version can assess a patient's lifetime suicidality for data collection purposes as well as eligibility based on inclusion/exclusion criteria.
2. The 'Since Last Visit' version of the scale assesses suicidality since the patient's last visit. This version is meant to assess patients who have completed at least 1 initial C-SSRS assessment and should be used in subsequent visits. The 'Since Last Visit' version of the C-SSRS is inquiries about any suicidal thoughts or behaviors the patient/participant may have had since the last time the C-SSRS was administered.

A frequency and percentage table and a shift from baseline by visit will be provided to display the number of patients who have answered at least one 'Yes' to: Suicidal Ideation (1-5),

Suicidal behavior (6-10), either have suicidal ideation or suicidal behavior (1-10), and the question “Non-Suicidal Self-Injurious Behavior”.

In details, the Suicidal Ideation and Suicidal behavior will include questions as below:

Suicidal Ideation (1-5)

1. Wish to be dead
2. Non-Specific thoughts
3. Ideation without intent to act
4. Ideation with some intent to act
5. Ideation with specific plan

Suicidal behavior (6-10)

6. Preparatory acts or behavior
7. Aborted attempt
8. Interrupted attempt
9. Actual attempt
10. Completed suicide

All C-SSRS data will be listed.

N. Patient Health Questionnaire-9 (PHQ-9)

The PHQ-9 is a 9-item depression scale of the Patient Health Questionnaire and will be used for patients ≥ 12 years of age. After the patient has completed the PHQ-9 questionnaire, it is scored by the trial staff. Any patient with a PHQ-9 score ≥ 10 will be referred to a mental health professional (MHP). The PHQ-9 will be administered according to the SOA.

Summary statistics for the score of summation of the 9 items and changes from baseline will be provided. Frequency count and percentage of number of patients with score ≥ 10 will also be included. Only scores with all 9 items answered will be summarized.

All PHQ-9 data will be listed.

O. Children’s Depression Inventory-2 (CDI-2)

The CDI-2 has both a self-report and a parent version.

The CDI-2: Self-Report Short version is an efficient screening measure that contains 12 items and will be administered to patients < 12 years of age according to the SoA.

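### A C-SSRS or injection-site finding recorded only at an unscheduled or early-termination visit is left out of the by-visit safety tables whenever that window's scheduled visit took place

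*SAP*

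**What the plan says.** The rule stands under Missing Data, Analysis Window, in SAP V.E, within the general analytical considerations:

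- Scope: "All measurements recorded at unscheduled or early termination visits will be mapped according to the windowed visits by actual study day".
- Use: "These records then will be used for analysis if the scheduled ones are missing".
- Tie-break: "If more than one visit occurs within a single visit window, then the analysis will take the one closest to and before the target day".
- Scheduled assessments stay at their protocol visit whatever the actual study day.

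The safety tables that depend on it are these:

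- **Injection site (SAP IX.C):** severity by stage and visit, with patients assessed at that visit as the denominator.
- **Laboratory (SAP IX.D):** values and changes by stage and visit, following the schedule of assessments. Shift tables within stage are added, with no statement of which record is used.
- **C-SSRS (SAP IX.M):** "A frequency and percentage table and a shift from baseline by visit will be provided".

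The protocol expects off-schedule assessments. Section 8.9.8 says of injection sites that "unscheduled evaluations may also be recorded as warranted by clinical conditions". Appendix 4 requires assessment at the scheduled times "and in the setting of any injection site reaction adverse experience". Section 8.9.5 calls for repeat testing of clinically significant laboratory abnormalities. Sections 5.2 and 6.3 require an early-termination visit, and Tables 1 and 2 include injection site, C-SSRS, laboratory tests and ECG at that visit.

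**The concern.** An unscheduled safety assessment is usually made because something has happened. A rule that keeps the scheduled record and drops the extra one therefore tends to drop positive findings, so the by-visit tables lean towards normal.

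C-SSRS is the clearest case. Footnote 14 to Protocol Table 2 says the 'Since Last Visit' "version of the scale will be used to assess suicidality since the last time the C-SSRS was administered". If ideation is recorded at an extra visit, the next scheduled form asks only about the time after that visit. A truthful 'No' then goes into the table and the earlier 'Yes' goes nowhere in it. Had the site not given the extra form, the scheduled form would have covered the same event. Closer monitoring can thus lower the tabulated count.

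Early termination matters as well. Protocol 6.3 expects some patients to stop because of injection-site reactions, and their last assessment falls under the same rule.

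**Working it through.** The plan gives no figure to reproduce. The check applies the V.E rule to the SAP window table and to Protocol Tables 1 and 2.

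**Inputs.** Windows, with target day in brackets:
- Stage 1: V2 2–21 (14), V3 22–35 (28), V4 36–49 (42), V5 50–70 (56), V6 71–98 (84), V7 99–117 (112).
- Stage 2: V8 113–133 (126), V9 134–154 (140), V10 155–182 (168), V11 183–210 (196), V12 211–238 (224), V13 239–266 (252), V14 267–283 (280).

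Assumptions: Stage 2 dosing starts on Day 112; Day 266, which the table gives to both V13 and V14, is counted once under V13. The totals are 117 − 2 + 1 = 116 days in Stage 1 and 283 − 113 + 1 = 171 days in Stage 2.

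**1. Days whose window holds a scheduled record.**
- Injection site and C-SSRS are scheduled at every one of these visits: 116/116 and 171/171, or 100%.
- Laboratory tests are scheduled at V5 and V7 (21 + 19 = 40; 40/116 = 34%) and at V10, V12 and V14 (28 + 28 + 17 = 73; 73/171 = 43%).

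**2. The rule applied to one patient.** Injection site is 'none' at the scheduled Day 28 visit and 'severe' at an unscheduled visit on Day 33. Both days map to 22–35. The Week 4 table shows 'none'. It would show 'severe' only if the Day 28 record were missing.

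**3. The same dates for C-SSRS.** The form is negative on Day 28, positive at the extra visit on Day 33, and negative on Day 42. The Day 42 form covers only the time since Day 33. The Week 4 and Week 6 rows both show no event.

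**4. Early-termination visits.** Suppose scheduled visits take place on their target days. An early-termination record is displaced if it falls after the target day but within the same window.
- Stage 1, Days 2–111 (110 days): 7 + 7 + 7 + 14 + 14 = 49 days; 49/110 = 45%.
- Stage 2, Days 113–279 (167 days): 7 + 14 × 5 = 77 days; 77/167 = 46%.

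**5. Laboratory tests separately.** In a window with a scheduled draw, an unscheduled result is displaced as above. In the other windows nothing displaces it; a table laid out by the schedule of assessments simply has no row for it. An abnormal value from a scheduled draw stays in the table, and only its repeat drops out.

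**6. Search for a summary that would recover the finding.** The readable safety sections contain no worst post-baseline or any-time-on-treatment summary for these assessments. The most severe outcome in the skin examination (SAP IX.I) is taken across skin regions and reported by visit, not across time.

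**The case against.** **The adverse event tables already show these events.** This largely stands for clinically significant findings. Protocol Appendix 5 makes a clinically significant abnormal safety assessment an adverse event and grades injection-site reactions. The SAP tabulates treatment-emergent events by maximum CTCAE grade within stage, without visit windows. Appendix 4's own trigger for an extra injection-site assessment is an adverse experience. A reader might infer that all safety summaries lose these events; they do not. The route is weaker for C-SSRS. Nothing in the documents requires a positive form to be recorded as an adverse event, and ideation of types 1 to 3 is not among the referral triggers in Protocol 8.9.9.

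**The safety endpoint is not affected.** A reader might infer that a named endpoint is biased. It covers adverse events, vital signs and laboratory changes (Protocol Table 3). C-SSRS and injection-site tables, where displacement is fullest, are not named in it.

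**The SAP does not breach the protocol.** Protocol 10.3 says "change from baseline to any post-dose values will be summarized for vital signs and clinical laboratory results", which could be read as a promise to use every value. The preceding sentence there speaks of summaries by time of collection, so change at each planned time point is an equally fair reading. A conflict is arguable, not shown.

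**Sparse laboratory draws are a separate matter.** Scheduled draws from Week 8 onwards are eight weeks apart and can miss short abnormalities. That is a property of the schedule and would be the same without V.E.

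**Wording and redaction.** The tie-break might let an unscheduled record beat a late scheduled one, but it still selects by timing and never by severity. In SAP IX.M, 'by visit' may attach only to the shift table; even so, no text brings unscheduled records into the frequency table. The opening of SAP section IX is redacted, so an exemption there cannot be excluded.

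**Other safeguards.** All recorded data are listed (SAP V.N), and the DSMB receives C-SSRS, injection-site and laboratory data (SAP V.I). The C-SSRS loss also needs an extra form that is positive while the scheduled forms are negative.

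**Conclusion.** The point holds for the descriptive by-visit tables. On the natural reading of V.E, a C-SSRS or injection-site finding made only at an unscheduled or early-termination visit is omitted whenever the scheduled assessment in that window exists, and every post-baseline window has one scheduled. For laboratory results the omission is partly displacement and partly the table layout.

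The percentages above are shares of calendar days exposed to the rule. They are not estimates of how many findings would be lost: the documents do not say how often extra assessments occur, so the under-count cannot be sized. The early-termination shares also assume visits on target days.

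No data are lost, the primary endpoint is untouched, and the trial plans no statistical testing (SAP V.K). Severity is minor to moderate, resting mainly on C-SSRS and then injection site, and on there being no exemption in the redacted text.

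**What to change.** 1. State in SAP V.E that the preference for scheduled records applies to efficacy analyses and to by-visit descriptive statistics.
2. Add a worst post-baseline summary within each stage, using all scheduled, unscheduled and early-termination records: any C-SSRS ideation or behaviour, maximum injection-site severity, and laboratory shift to worst value. Do likewise for ECG, PHQ-9 and skin examination.
3. Use the laboratory part as the stated basis for the protocol's commitment (section 10.3) to tabulate how many patients have abnormal safety laboratory results.

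The cost is one SAP paragraph, one derived record per parameter and a little programming. No new data are needed. Abnormal counts will be slightly higher than under the present rule. The change is best made before the Stage 1 analysis described in SAP V.J.

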2. SCHEDULE OF ASSESSMENTS

Table 1: Schedule of Assessments – Stage 1

Assessment	Screening (In-Person)	Enrollment Visit (IP)	Phone Call†	Virtual Trial Visits	In-Person Trial Visits	Early Termination Visit (In-Person)
Visit Number		V1	V1c	V2, V3, V4, V6	V5, V7	
Study Week			1	2, 4, 6, 12,	8, 16	
Study Day	-56 to -14	1	7	14*, 28, 42, 84	56, 112	
Window			+/-2	+/-3	+/-5	+/-5
Informed Consent/Assent (1)	X					
Inclusion/Exclusion	X	X				
Genetic Sample (2)	X	X				
Optional WES (3)	X	X				
Medical History	X	X				
Nutrition and physical activity counseling and follow-up		X	X	X	X	
Physical Exam (4)	X	X			X	X
Fitzpatrick Classification Scale	X					
Comprehensive Skin Exam (5)	X				X	X
Weight (6)	X	X		X	X	X
Height (7)	X	X			X	X
[REDACTED]						
Vital Signs (9)	X	X		X	X	X
ECG (10)	X				X	X
Pregnancy (11)	X	X		X	X	X
Hunger Questions (12)	X	X		X	X	X

Table 1: Schedule of Assessments – Stage 1

Assessment	Screening (In-Person)	Enrollment Visit (IP)	Phone Call†	Virtual Trial Visits	In-Person Trial Visits	Early Termination Visit (In-Person)
Visit Number		V1	V1c	V2, V3, V4, V6	V5, V7	
Study Week			1	2, 4, 6, 12,	8, 16	
Study Day	-56 to -14	1	7	14*, 28, 42, 84	56, 112	
Window			+/-2	+/-3	+/-5	+/-5
[REDACTED]						
Global Hunger Questions (15)		X		X (14)	X	X
C-SSRS (16)	X	X		X	X	X
PHQ-9 (23)	X	X		X	X	X
CDI-2 (24)	X	X		X	X	X
[REDACTED]						
[REDACTED]						
Adverse Events	X	X	X	X	X	X
Injection Site Inspection		X		X	X	X
Concomitant Medication Review	X	X	X	X	X	X
Safety Laboratory Tests (17)	X				X	X
[REDACTED]						
[REDACTED]						
Trough PK (18)		X			X	X
Anti-Drug Antibodies (19)	X				X	X
Biomarkers (20)		X			X	X
Daily Drug Compliance (21)		X		X	X	

Table 1: Schedule of Assessments – Stage 1

Assessment	Screening (In-Person)	Enrollment Visit (IP)	Phone Call†	Virtual Trial Visits	In-Person Trial Visits	Early Termination Visit (In-Person)
Visit Number		V1	V1c	V2, V3, V4, V6	V5, V7	
Study Week			1	2, 4, 6, 12,	8, 16	
Study Day	-56 to -14	1	7	14*, 28, 42, 84	56, 112	
Window			+/-2	+/-3	+/-5	+/-5
Dispense/Return Trial medication (22)		X		X	X	X

Abbreviations: ADA = anti-drug antibodies; CDI-2 = Children’s Depression Inventory -2; C-SSRS = Columbia Suicide Severity Rating Scale; ECG = electrocardiogram; [REDACTED] IP = In Person; [REDACTED]

[REDACTED]; PHQ-9 = Patient Health Questionnaire-9; PK = pharmacokinetic; QoL = quality of life; WES = Whole Exome Sequencing.

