5.2. Patient and Trial Completion

A patient is considered to have completed the trial if he/she has received the last planned dose of trial medication on Study Day 280 and completed the EOS telephone visit on Day 308.

Patients who discontinue before completing the Study Day 280 EOT visit are to attend an Early Termination visit within 14 days (± 7 days) after the last dose of trial medication for final trial assessments.

The end of the trial is defined as the date of the last visit of the last patient under the auspices of the current trial.

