6.3. Treatment Discontinuation and Withdrawal from the Trial

Given this rare patient population, every effort should be made to encourage and keep patients enrolled in the trial until completion, unless there are any safety concerns necessitating withdrawal of the patient. The Sponsor will provide assistance for patient and caregiver travel and will provide other necessary logistical support to ease the burden on the patient in order to facilitate compliance and completion of trial participation.

Discontinuation of trial treatment or skipped visits/injections may be allowed without withdrawal from the trial.

Some patients' reason for discontinuation may be related to injection site reactions and burdensome laboratory/visits. Patients can be offered the option to discontinue trial medication but remain in the trial. These patients who stop therapy will be counted as a non-responder, irrespective of treatment assignment. However, they will be followed and have weight assessments at each visit, particularly at the final visit to determine weight trajectory for all patients. Patients who withdraw before completing Visit 14 are to attend an Early Termination visit within 14 days (± 7 days) after the last dose of trial medication for final trial assessments. If possible, patients will be asked to determine weight assessment at the expected time of their EOT visit.

If the patient withdraws consent for disclosure of future information, the Sponsor may retain and continue to use any data collected before such a withdrawal of consent.

If a patient withdraws from the trial, he/she may request destruction of any samples taken and not tested, and the Investigator must document this in the site trial records.

Patients will be informed that they have the right to withdraw from the trial at any time for any reason, without prejudice to their medical care. The Investigator also has the right to withdraw patients from the trial for reasons such as:

- AEs, which in opinion of Investigator justifies treatment or trial withdrawal. For specific predefined events, additional monitoring and guidance for the Investigator is provided in [Appendix 5](#).
- Non-adherence to trial medication regimen or protocol requirements.
- Non-compliance with instructions or failure to return for follow-up.

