1	Virtual Visit 6	12	84	71 - 98
1/2	In-Person Clinic Visit 7	16/End of Stage 1	112	Patients enrolling in Stage 2: 99 to first dose of Stage 2 Patients not enrolling in Stage 2: 99 - 117
2	Virtual Visit 8	18	126	Post-dose - 133
2	Virtual Visit 9	20	140	134 - 154
2	In-Person Clinic Visit 10	24	168	155 - 182
2	Virtual Visit 11	28	196	183 - 210
2	In-Person Clinic Visit 12	32	224	211 - 238
2	Virtual Visit 13	36	252	239 - 266
2	End of Treatment Visit 14	40	280	266 - 283

Primary Efficacy Endpoint Missing Data Imputation

For patients who do not have BMI value at the end of Stage 1 (Week 16), the unscheduled or early termination weight measurement mapped into Week 16 per visit window will be used for the primary analysis. If weights are measured in triplicate within a same date, the average of the triplicates will be calculated before the BMI calculation. The latest height value will be used together to derive the missing Week 16 BMI.

For patients who still do not have BMI value after above imputation at Week 16, they are treated as non-responder for the primary.

Missing or Partial Adverse Event and Medication Start or Stop Date:

For partial start dates:

- If the year is unknown, no imputation will occur.
- If the year is known and the month and day is unknown, then:
 - If the year matches the year of the first dose date, then impute the month and the day the same as first dose date.
 - If the year is not the same year of the first dose, then month and day will be imputed as 01 January.
- If the month and year is known and the day is unknown, then:
 - If the month and year match the month and year of the first dose date, then impute the day the same as first dose date.
 - If year and month is not the same as the first dose date, then the day will be imputed as "01".

For partial end-dates:

- If the year is missing, no imputation will be performed, and the AE/CM will be assumed as ongoing.
- If the year is present and both month and day are missing and the year is not the same as the last study date, then the month and day will be imputed as the last day of the year, 31 December.
- If the year is present and both month and day are missing and the year is the same as the last study date, then the month and day will be imputed as the last study date.
- If the year and month are present and only the day is missing, and the year and month is not the same as the last study day then the day will be imputed as the last day of the month.

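### The Week 16 window for early termination weights closes on Day 117, so some late Stage 1 withdrawals with an on-time clinic weight are scored as non-responders

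*SAP*

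**What the plan says.** **SAP V.E, Analysis Window.** ET and unscheduled weights are placed by the day on which they were taken: "All measurements recorded at unscheduled or early termination visits will be mapped according to the windowed visits by actual study day". Scheduled visits are not bound by the windows: "All scheduled assessments will be analyzed according to the protocol defined visits, regardless of the study day". The Week 12 window is Days 71-98. The Week 16 row then reads "Patients not enrolling in Stage 2: 99 - 117".

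**SAP V.E, Primary Efficacy Endpoint Missing Data Imputation.** An ET or unscheduled weight that maps to Week 16 replaces a missing Week 16 value. For patients still without a BMI, "they are treated as non-responder for the primary".

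**Protocol 5.2.** Patients who discontinue early are to "attend an Early Termination visit within 14 days (± 7 days) after the last dose of trial medication". Section 6.3 repeats this for anyone withdrawing before Visit 14, so it covers Stage 1. The Window row of the Stage 1 Schedule of Assessments shows +/-5 for the same visit.

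**SAP Estimand table (before section III).** Treatment discontinuation is handled by treatment policy.

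**Protocol 6.3.** Patients who stop drug but stay in the trial count as non-responders, yet are still weighed at each visit. Withdrawn patients are asked, where possible, for a weight when their EOT visit would have been due.

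**The concern.** The Day 117 limit is the Visit 7 tolerance. Visit 7 itself does not need it, because scheduled visits count whatever day they fall on. The limit therefore binds only on ET and unscheduled weights. ET visits follow a different clock, which runs from the last dose.

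The window is also lopsided. It accepts a weight 13 days before Day 112 but only 5 days after it. A patient who withdraws shortly before Week 16 and attends ET on time can have an in-clinic weight discarded and replaced by failure, while a patient who stopped somewhat earlier is scored on what was measured. This touches the primary endpoint, which is reported by gene with up to 10 patients planned per gene (Protocol 5.1.4). A treatment-policy estimand would ordinarily use an observed weight near Week 16.

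**Working it through.** **1. Where Day 117 comes from.** Visit 7 is due on Day 112 with a window of 5 days: 112 + 5 = 117, the SAP's upper bound. The lower bound follows the Week 12 window: 98 + 1 = 99. Reach before target: 112 - 99 = 13 days. Reach after target: 117 - 112 = 5 days.

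**2. ET at exactly 14 days.** Let L be the day of the last dose, from 1 to 111. The ET weight counts if 99 ≤ L + 14 ≤ 117, that is, 85 ≤ L ≤ 103.

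- L = 85-103: ET on Days 99-117, so the measured weight is used.
- L = 104-111: ET on Days 118-125, so the patient is a non-responder. These visits lie 6 to 13 days from Day 112, no further away than the accepted Day 99.
- L ≤ 84: ET by Day 98. The weight maps to Week 12 or earlier, so the patient is again a non-responder.

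**3. Other readings of the ET rule.** The protocol wording can mean a visit centred on 14 days or a deadline. For each L from 104 to 111, count the compliant days after Day 117 and pool over the eight values of L. Treating compliant days as equally likely is an assumption.

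| ET allowed after last dose | Late / compliant day combinations | Share late | Last-dose days always lost |
|---|---|---|---|
| +7 to +21 (14 ± 7) | 92 / 120 | 77% | 111 |
| +9 to +19 (14 ± 5, schedule) | 73 / 88 | 83% | 109-111 |
| 0 to +21 | 92 / 176 | 52% | none |
| 0 to +14 | 36 / 120 | 30% | none |

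Example for the first row: the late count at each L is L + 21 - 117 = L - 96. This runs from 8 to 15 out of 15, and the counts sum to 92.

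**4. Who is exposed under 14 ± 7.** A late visit is possible when L + 21 > 117, so from L = 97. It is certain when L + 7 > 117, so only at L = 111. Use of the weight is certain when L + 7 ≥ 99 and L + 21 ≤ 117, so L = 92-96.

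**5. Effect of one patient.** In a single-gene display of 10, moving one patient who lost at least 5% from responder to non-responder changes 5/10 (exact 95% CI 18.7-81.3%) to 4/10 (12.2-73.8%). In a group of n the shift is 1/n.

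**6. Stage 2 rows.** Visit 13 is given as Days 239-266 and Visit 14 as Days 266-283, so Day 266 belongs to both.

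**The case against.** The best defence is that the rule is pre-specified and conservative. Treatment policy asks for the outcome at the end of Stage 1, and a weight from Days 118-132, taken off drug, is an imperfect stand-in. That is fair as far as it goes. But the SAP already accepts weights 13 days early. Under 14 ± 7 it also accepts ET weights up to 21 days off drug (last dose Day 96, ET on Day 117).

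Second, Protocol 6.3 supplies other weights. Patients who stay in the trial are weighed at Visit 7, and withdrawn patients are asked for a weight at their expected EOT time. This stands as a limit on scope: only withdrawals with no Visit 7 weight and no other weight on Days 99-117 are affected. The safeguard is incomplete, because the request applies only where possible and Protocol 5.1.3.1 gives two EOT days, 112 and 280.

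Third, for patients who stop drug but remain in the trial, non-response is the protocol's own rule. That is true, but it conflicts with the SAP estimand.

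Three stronger readings are tempting, and the documents do not support them:

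- *Everyone stopping on Days 104-111 becomes a non-responder.* This is exact only for ET at 14 days. Under 14 ± 7 only Day 111 is always lost, and under the deadline readings no day is.
- *Earlier stoppers in general are scored on measured weight.* At nominal timing this holds only for Days 85-103. Those stopping by Day 84 also fail, so a middle band is favoured over both sides.
- *A scheduled EOT on Days 284-285 (280 + 5 = 285) is lost because the Visit 14 window ends on Day 283.* It is not lost, since scheduled visits count whatever their day. That limit matters only for ET and unscheduled weights, and the Stage 2 efficacy text is too heavily redacted to judge the effect.

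**Conclusion.** The mismatch is real but narrow. Some late Stage 1 withdrawals will have a protocol-compliant clinic weight discarded and be counted as failures. For last doses on Days 104-111, the share of compliant ET days falling after Day 117 is 30% to 83% across the readings of the ET rule, if compliant days are equally likely. Under 14 ± 7, patients stopping from Day 97 are exposed.

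The documents give no withdrawal rate, so the number of patients cannot be computed; it is probably small. The bias runs toward a lower response rate, and only a patient who actually lost at least 5% is misclassified. One such patient shifts a 10-patient single-gene result by 10 points. The shift is smaller in larger pooled groups: SAP V.Q combines 13 genes in the SEMA3 cohort and 14 in Other. There is no hypothesis test to be affected. This is a cheap improvement to the SAP and does not undermine the design.

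**What to change.** In the SAP V.E window table:

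- For ET and unscheduled weights of patients not entering Stage 2, extend the Week 16 upper bound from Day 117 to Day 132 (last dose Day 111 + 21 days). This covers every reading above, since the others end at 111 + 14 = 125 or 111 + 19 = 130. Keep non-responder imputation for patients with no weight in the extended window.
- Start the Visit 14 window on Day 267, to remove the overlap with Visit 13. Any later upper limit for Visit 14 would concern ET and unscheduled weights only.

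Two conflicts should be reconciled at the same time: the Protocol 6.3 non-responder statement against the SAP treatment-policy estimand, and the ± 7 days in Protocol 5.2 and 6.3 against the +/-5 in the schedule.

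The window change costs a few table cells and needs no new data. Its small downside is that some Week 16 values will be off-drug weights taken up to 20 days after Day 112 (132 - 112). It does not help patients whose ET visit falls before Day 99, who remain non-responders.
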